## **5            STUDY POPULATION CHARACTERISTICS**

### **5.1        Subject disposition**

The number of patients enrolled, eligible, those that have completed each post-baseline visit as well as those prematurely withdrawn, along with the reasons for study withdrawal will be presented. Also, the eligible and non-eligible patients per participating site will be tabulated.

### **5.2        Protocol deviations**

All protocol deviations resulting in patients' exclusion from the analysis will be reported in the CSR. More specifically, a listing with deviators will be created containing site number, patient number and description of deviation.

## **6            PATIENT CHARACTERISTICS**

### **6.1        Sociodemographic and anthropometric characteristics**

Descriptive statistics ( $n_{pt}$ ,  $n_{miss}$ , mean, SD, median, 25th and 75th percentiles, min and max) will be presented for patients' age at the time of enrolment. Patient distribution by gender, race, place of residence, educational level, marital status, employment status will be presented in frequency tables ( $n_{pt}$ , %).

Summary statistics will be presented for body weight (kg), height (cm), BMI ( $\text{kg}/\text{m}^2$ ) at baseline. Body weight (kg) and BMI ( $\text{kg}/\text{m}^2$ ) will also be summarized for the predefined post-baseline time points along with the changes from enrolment. In addition, patient distribution per BMI categories at enrolment and at post-baseline time points will be displayed using absolute and relative frequencies.

## Statistical Analysis Plan

In regards to smoking history, the distribution of patients per smoking status at enrolment will be displayed in a frequency table ( $n_{pt}$ , %). Pack-years of smoking will be presented with the use of summary statistics for current and former smokers, while the time since smoking cessation and years of smoking will be summarized for former and occasional smokers, respectively. In addition, the number and proportion of patients that changed their smoking habits from enrolment to the end of observation period or to the time of premature withdrawal as well as the type of change and smoking status at the end of observation period/withdrawal will be presented.

### 6.2 NSCLC disease characteristics

The age at initial diagnosis of NSCLC, the age at diagnosis of locally advanced or metastatic NSCLC, the time from initial diagnosis of NSCLC to locally advanced or metastatic NSCLC diagnosis as well as the time from diagnosis of locally advanced/metastatic NSCLC to enrolment will be summarized.

In regards to the initial diagnosis of NSCLC, the distribution of patients per type of diagnosis, per stage of diagnosis, per primary tumor localization as well as per histologic classification will be tabulated in frequency tables ( $n_{pt}$ , %).

Moreover, the NSCLC stage along with the TNM staging at the time of afatinib initiation and the sites of metastases (*only for patients with  $T_{any}N_{any}M1b$  stage*) will be presented by absolute and relative frequencies. The total number of metastatic lesions for patients with *stage IV disease* will be presented by using summary statistics ( $n_{pt}$ ,  $n_{miss}$ , mean, SD, median, 25th and 75th percentiles, min and max). Patients distribution per EGFR mutation location and mutation type as well as per method of identification of the EGFR mutation(s) will be displayed by frequency tables ( $n_{pt}$ , %).

Finally, the distribution of patients per disease stage at the end of study observation period or at the time of premature withdrawal will be displayed in frequency table ( $n_{pt}$ , %). The change in disease stage from study treatment initiation to end of study observation period/ premature withdrawal will be presented by shift table.

In addition, patient distribution ( $n_{pt}$ , %) by change in the disease status (improvement, stable, progression) from baseline and evaluation criteria (imaging, clinical, laboratory) at each of the post-baseline timepoints will be presented. The number and proportion of patients with progression with at least one of the evaluation methods; with improvement with any of the evaluation methods and no progression as well as with stable status with no progression/improvement according to the available evaluation methods at each post-baseline timepoints will be presented in frequency tables ( $n_{pt}$ , %). In regards to patients with improvement with at least one evaluation method and no progression, the combinations of the disease statuses with each evaluation (imaging, clinical, laboratory) method will be presented in absolute and relative frequencies. For patients for whom a change in the disease status was identified using an imaging method summary statistics will be presented for the number of metastatic lesions at the time of improvement or deterioration, along with the change from baseline; in addition, for patients with a deterioration the new metastatic sites will be

## **Statistical Analysis Plan**

presented (as applicable), while for those with improvement the changes in the metastatic sites will be presented. Finally, the number and proportion of patients with at least one progression as well as those with at least one improvement as assessed using an imaging method over 6, 12, 18, 24, 30, 36, 42 and 48 months and throughout the study observation period will be displayed.

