In the LUX-Lung 3 RCT, patients were randomised (2:1) to receive afatinib 40 mg once daily or up to 6 cycles of pemetrexed/cisplatin. According to the results of the study, for the subgroup of patients with common mutations (Del 19, L858R) (204 on afatinib and 104 on chemotherapy) the median PFS was 13.6 versus 6.9 months [Hazard Ratio (HR) 0.47; 95% CI 0.34-0.65;  $P<0.0001$ ] and the median OS was 30.3 versus 26.2 months, demonstrating a clear benefit of afatinib treatment. In addition to the Del 19, L858R mutations, certain less common mutations have also been shown to be sensitive to afatinib treatment [29]. Moreover, compared to chemotherapy first-line afatinib was associated with better control of cough (HR, 0.60; 95% CI, 0.41 to 0.87;  $P=0.007$ ) and dyspnea (HR, 0.68; 95% CI, 0.50 to 0.93;  $P=0.015$ ), as well as improved global health status/QoL ( $P=0.015$ ), and functional scale scores as assessed with the use of EORTC QLQ-C30 and the EORTC-QLQ-L13 [30]. Among the functional scale scores, physical ( $P<0.001$ ), role ( $P=0.004$ ), and cognitive ( $P=0.007$ ) functioning were improved compared to chemotherapy.

The results of the pivotal LUX-Lung 3 RCT have been supported by the LUX-Lung 6 RCT conducted in 36 sites in China, Thailand and South Korea among 364 patients. The study compared first line afatinib with gemcitabine/cisplatin chemotherapy. In the afatinib arm, mean PFS was 11.0 months vs. 5.6 months for those in the chemotherapy arm (HR 0.28;  $P<0.0001$ ). In addition, a significant higher proportion of patients demonstrated improvement of cough ( $P<0.0001$ ), dyspnea ( $P<0.0001$ ) and pain ( $P=0.03$ ), while afatinib also delayed the time to deterioration of these symptoms. Global health improvement was also demonstrated by a higher proportion of patients in the afatinib group than in the gemcitabine and cisplatin group (62·7% versus 32·7%;  $P<0.0001$ ). Notably, prolongation of PFS was associated with improved HRQoL and significantly longer control of disease-related symptoms [3].

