#### **11.5 DATA SOURCES**

The study will mainly involve new data collection, by means of a web based data capture (WBDC) system. Data will be collected by the study physicians as generated according to the standard clinical practice and by the patients as captured with the use of PROs. No further laboratory tests and examinations are required apart from those recommended by the study medication SmPC.

Patient source data pertaining to medical- and lung cancer-related history will be abstracted from patient medical charts/records by the investigators and will be recorded in the relevant section of the WBDC.

All afatinib treatment modifications, concomitant medications, study-related routine clinical assessments, adverse events (AEs) and vital status will also be collected. Regarding vital status, if a patient is prematurely withdrawn from the study, he/she will be contacted by telephone or other methods to assess vital status at the end of study unless the patient has actively withdrawn consent for all forms of contact (refer to section [11.2.4.3](#)).

Concomitant or prior disease-related medications entered into the database will be coded using the Anatomical Therapeutic Chemical (ATC) WHO Collaborating Centre for Drug Statistics Methodology (WHOCC) Drug Reference List.

Medical history/comorbidities and adverse events will be coded using Medical Dictionary for Regulatory Activities (MedDRA) terminology.

In addition, physicians will be requested to assess:

- **Patients' performance status** using the ECOG PS instrument. (*For a sample of the English version please refer to [ANNEX 3: ECOG PERFORMANCE STATUS SCALE](#)*).

Furthermore, the **following PROs** will be collected via self-administered paper questionnaires completed by the patients themselves at study enrolment and periodically throughout study participation, according to the study visit frequency.

- **Disease-specific symptoms** will be measured using the self-administered patient-rated LCSS, a reliable and valid lung cancer-specific instrument that is comprised of two components, the patient-rated scale employed in the present study and the observer-rated [\[20, 36, 37\]](#).

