## Statistical Analysis Plan

**Figure 1: Synoptic Study Diagram**

A total of 128 patients are planned to be enrolled by seven (7) Oncology and Pulmonology hospital centres/clinics in Greece specialized in lung cancer.

The overall study duration period is expected to be 60 months, including a 48-month enrolment period and a minimum 12-month follow-up period. During the observation period, data will be collected at routine clinical visits at 2-month intervals for the first 12 months and at 6-month intervals thereafter until the end of study participation.

In the context of this study which is planned to have an overall duration of 60 months, each participant will be treated with afatinib and observed in the context of the study until the end of study participation defined as a maximum of 48 months after afatinib treatment initiation or until disease progression, death, withdrawal of consent, unacceptable toxicity, study completion or physician's decision whichever occurs earlier. The maximum 48-month length of participation in the study pertains to the patients enrolled during the first 12 months of recruitment, while the maximum observation period for the last patient enrolled is 12 months.

Being non-interventional and observational in nature, this study does not impose any diagnostic/therapeutic interventions or strict visit schedule. Patients will be treated as per the routine medical practice in terms of visit frequency, types of assessments performed and with

[figure not shown]

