### 3.5 Analysis sets

In accordance to the non-interventional design of the study, all statistical analyses will be performed in the Full Analysis Set (FAS) comprised of all eligible subjects who have been enrolled in the study, regardless of whether or not they have finally completed their projected participation in the study.

The analysis of the primary objective of the study will be performed in the Per Protocol Set (PPS) which will include all eligible study patients with available data pertaining to the study primary endpoint, i.e. 6-month symptom improvement rate as per the LCSS ASBI score. In case that the size of the PPS differs substantially (i.e.  $\geq 20\%$ ) from the size of the FAS, then descriptive statistics of demographic and baseline disease and clinical characteristics will also be presented in the PPS.

Subsets of FAS with available data will also be created and analysed for the purposes of secondary endpoint analyses. The safety analysis will also be applied in the FAS.

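### SAP 6.2 gives no denominator or follow-up rule for imaging progression over 6 to 48 months; under the default FAS rule the figures from 18 months on are too low as risks

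*SAP*

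**What the plan says.** SAP 6.2 ends with two percentages, patients with one or more progressions and patients with one or more improvements, "as assessed using an imaging method over 6, 12, 18, 24, 30, 36, 42 and 48 months and throughout the study observation period". It gives no denominator, at-risk set or censoring rule for any horizon.

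The general rule in SAP 3.5 is that "all statistical analyses will be performed in the Full Analysis Set (FAS) comprised of all eligible subjects who have been enrolled in the study", whether or not they complete the study. Subsets with available data are foreseen there for secondary endpoints. Disease status is not a secondary endpoint (SAP 2.1.2); Protocol 11.4.3 lists it among the other variables. SAP 4.2 deals with partial dates and the primary endpoint. The one censoring rule in the available SAP text is for adverse-event incidence rates (SAP 9.2).

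On follow-up, SAP 2.3 sets 48 months of enrolment in a 60-month study. It adds that "The maximum 48-month length of participation in the study pertains to the patients enrolled during the first 12 months of recruitment", and that the last patient is observed for at most 12 months. Observation also stops at "disease progression, death, withdrawal of consent, unacceptable toxicity, study completion or" physician's decision.

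SAP 5.1 will tabulate "those that have completed each post-baseline visit as well as those prematurely withdrawn", with reasons for withdrawal.

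**The concern.** A percentage labelled as over 36 months is naturally read as the share of patients who have progressed by 36 months. Computed on the whole FAS, it counts as not progressed anyone whose observation ended earlier, including patients who enrolled too late to be observed for 36 months. The result then depends on the recruitment calendar and on early exits as well as on the disease. The figure for the whole observation period does not have this problem, because it is an honest count of what was seen.

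What is at stake is the reading of long-horizon real-world progression figures in a study meant to complement the randomised evidence. Nothing in the primary endpoint or sample size depends on them.

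**Working it through.** **Plan figures.** 48 months of enrolment + 12 months of minimum follow-up = 60 months, and 60 − 12 = 48 months of maximum participation, so SAP 2.3 is consistent with itself. The planned number also follows: 96 / (1 − 0.25) = 128. The plan gives no expected progression percentage to reproduce.

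**Inputs.** From the documents: 128 patients, the timeline above, and two PFS figures in Protocol 9.2.1. One is a median of 13.6 months (common-mutation subgroup of the phase 3 trial against pemetrexed/cisplatin). The other is 11.0 months (phase 3 trial against gemcitabine/cisplatin), worded as "mean PFS was 11.0 months vs. 5.6 months for those in the chemotherapy arm". Assumed: uniform accrual, exponential times, and PFS as a proxy for imaging progression. The figure of 11.0 is run first as a median and then as a mean.

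**Potential follow-up.** The share of patients who could be observed to horizon h ≥ 12 is s(h) = (60 − h)/48. This is 100% at 12 months, 87.5% at 18, 75% at 24, 62.5% at 30, 50% at 36, 37.5% at 42 and 25% at 48.

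**Risk and crude FAS percentage.** With λ = ln 2 / median:

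- True risk: 1 − exp(−λh).
- Crude FAS value for h ≥ 12: 1 − s(h)·exp(−λh) − [exp(−12λ) − exp(−λh)]/(48λ).

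Example for a median of 13.6 at 36 months: λ = 0.05097, exp(−12λ) = 0.5425, exp(−36λ) = 0.1596. Crude = 1 − 0.5 × 0.1596 − (0.5425 − 0.1596)/2.446 = 1 − 0.0798 − 0.1565 = 0.764. True = 0.840. The shortfall is 7.7 points before rounding.

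Staggered entry only, medians 11.0 / 13.6:

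| Months | True risk % | Crude FAS % | Shortfall, points | At risk of 128 |
|---|---|---|---|---|
| 12 | 53.1 / 45.8 | 53.1 / 45.8 | 0 / 0 | 60 / 69 |
| 18 | 67.8 / 60.0 | 67.0 / 59.2 | 0.9 / 0.8 | 36 / 45 |
| 24 | 78.0 / 70.6 | 75.2 / 67.8 | 2.7 / 2.8 | 21 / 28 |
| 30 | 84.9 / 78.3 | 80.0 / 73.1 | 4.9 / 5.2 | 12 / 17 |
| 36 | 89.7 / 84.0 | 82.7 / 76.4 | 6.9 / 7.7 | 7 / 10 |
| 42 | 92.9 / 88.2 | 84.2 / 78.2 | 8.7 / 10.0 | 3 / 6 |
| 48 | 95.1 / 91.3 | 84.9 / 79.2 | 10.3 / 12.1 | 2 / 3 |

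At risk = 128 · s(h) · exp(−λh).

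**11.0 read as a mean** (λ = 1/11): the shortfall is 2.3 points at 24 months and 4.9 at 36. Numbers at risk are then lower: 128 × 0.75 × exp(−24/11) ≈ 11 at 24 months and 128 × 0.625 × exp(−30/11) ≈ 5 at 30.

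**Sampling error.** In 3000 simulated Kaplan-Meier curves with 128 patients, the 95% half-width was 7.7 / 8.3 points at 24 months and 6.5 / 7.6 at 36. The shortfall is well inside sampling error at 24 months and about equal to it at 36.

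**Other exits.** The documents give no rate for this study; the 25% in the sample size concerns evaluability for the primary endpoint. If 5% to 20% of patients per year left independently for other reasons (assumed), with μ = −ln(1 − x)/12 added as a censoring rate, the 12-month figure would be 1.0 to 4.8 points low and the 24-month figure 5.4 to 13.5.

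**Improvement.** With progression as a competing event and an assumed median time to improvement of 4 to 12 months, staggered entry costs 0.4 to 2.5 points at 48 months (for example 52.8% against 50.3%).

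**The case against.** The strongest reply is that SAP 6.2 does not name the FAS. That stands: the denominator is inferred from SAP 3.5, so the downward direction holds under the default and is not written in 6.2. A programmer who kept only patients with an event or with full follow-up would err upward. At 36 months with a median of 13.6 that gives 76.4 / (76.4 + 8.0) = 90.5% against 84.0%. This does not rescue the plan, because an unstated denominator that can move the figure either way also needs settling.

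Second, the SAP does not call these figures risks. They sit among patient characteristics, and disposition will show follow-up thinning. This limits the reach of the point, but the disposition table does not correct the percentages.

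Third, a reader might take the 10 to 12 points at 48 months as the headline. That is not a fair summary. Only about 2 or 3 patients would be at risk, any sensible remedy would drop that horizon, and accrual shape alone moves the figure between about 4 and 19 points.

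Fourth, a reader might infer that a progression after withdrawal can never be counted, because Protocol 11.5 says of withdrawn patients that "he/she will be contacted by telephone or other methods to assess vital status at the end of study". The documents do not establish that. The sentence refers on to Section 11.2.4.3, which is not in the text available here, and neither is SAP Section 8.

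**Conclusion.** The point holds as a specification gap whose stated default gives a biased figure. Under SAP 3.5, the progression percentages from 18 months on understate the risk by that time: by about 1 point at 18 months, 3 at 24, 5 at 30 and 7 to 8 at 36, or 2.3 at 24 and 4.9 at 36 if 11.0 is a mean. These sizes rest on uniform accrual, exponential progression and PFS as a proxy. At 42 and 48 months the shortfall is larger, but there is no usable estimate to replace the crude figure.

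Three wider readings are not supported. The 6- and 12-month figures are not affected by staggered entry, only by other early exits of unknown frequency. Improvement is barely affected by staggered entry. A patient who dies without progression is not part of the error, since counting that patient as free of progression is correct for a cumulative incidence.

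The change is worth making but does not bear on the study's main result.

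**What to change.** In SAP 6.2, for each horizon:

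- Report the cumulative incidence of imaging progression with 95% CI and number at risk. Treat death as a competing event and censor event-free patients at their last imaging assessment.
- State how exits for progression judged only clinically or by laboratory are handled, since 6.2 uses three evaluation methods and SAP 2.3 ends participation at progression without naming a method.
- Omit or flag horizons with few at risk, for example under 10. On the medians above this removes 42 and 48 months, and 36 months under the shorter median. If 11.0 is a mean, it applies from 30 months.
- Keep the raw FAS counts, labelled as observed counts, beside the number still under observation. For improvement, these labelled counts are enough.

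The cost is a short SAP revision and standard competing-risk code. It needs dates of imaging assessment, progression and exit, which are assumed to be collected. Late intervals will be wide, and some bias remains if patients leave because progression is imminent.

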### **6.3 Physical examination and significant medical history/comorbidities excluding NSCLC**

The number and proportion of patients in which the physical examination was performed, those with at least one pathological finding and those with a normal physical examination in all examined major organs systems, will be calculated and presented at baseline. In addition, patients with pathological findings in each of the examined major organ systems will be presented.

Furthermore, the number and proportion of patients with no clinically significant diseases/medical conditions/surgeries at enrolment, those with at least one medical condition/comorbidity/surgery at enrolment as well as those with at least one ongoing medical condition/comorbidity will be calculated and presented.

Additionally, the depicting reported terms coded by MedDRA SOC and PT will be tabulated. Moreover, clinically relevant medical conditions will be presented separately with the use of frequency tables ( $n_{pt}$ , %) according to time of diagnosis ‘<6 months prior to afatinib initiation’, ‘6-12 months prior afatinib initiation’, ‘>12 months prior to afatinib initiation’, ‘Unknown’ as well as whether they are ‘Past’ or ‘Ongoing’ at time of afatinib onset and whether they are ‘Treated’ or ‘Not treated’ at the time of afatinib onset.

### **6.4 Prior and concomitant medications**

Number and proportion of patients with prior treatment for NSCLC at enrolment as well as the type of prior treatment (surgical intervention, radiotherapy, systemic chemotherapy, other-therapy) for NSCLC will be displayed in a frequency table ( $n_{pt}$ , %). Also, frequency tables ( $n_{pt}$ , %) will be presented for the reasons that surgeries were performed, for the type of radiotherapy and of discontinuation of the most recent chemotherapeutic regimen.

Summary statistics will be calculated for the number of surgical procedures and the number of previous chemotherapeutic regimens. In addition, the time elapsed from the most recent surgical procedure, from the most recent radiotherapy completion and from the discontinuation of the most recent chemotherapeutic regimen to afatinib treatment onset will be calculated and summarized.

[figure not shown]
Regarding concomitant medications with afatinib including radiotherapy, the number and proportion of patients receiving at least one concomitant therapy (pharmacological/non-pharmacological/radiotherapy), at least one pharmacological therapy and at least one non-pharmacological therapy (including radiotherapy) during the observational period will be calculated and presented. Frequency tables ( $n_{pt}$ , %) will be presented for the concomitant medications in terms of therapeutic subgroup and chemical substance (as coded by WHOCC ATC) and for radiotherapy, along with the indication/reason of receipt.

